#### 7.1.4 Treatment Period 2 (TP2)

TP2 is the second visit of the investigational phase. It takes place 2 to 7 days after TP1.

The following procedures and assessments will take place during this ambulatory visit:

|  |                      |
|--|----------------------|
| Clinical Study Code No.: CLI-05993AB6-07 | Version No.: 2.0     |
| EUDRACT No.: 2022-000536-36              | Date: 30 August 2022 |

- Study restrictions: study restriction criteria will be checked, according to [Section 7.2](#);
- Concomitant medications: concomitant medications taken by the subject since TP1 and during TP2 will be checked and recorded;
- AE recording: the status of AEs ongoing at TP1 will be checked and updated in the eCRF when applicable. Any new AE occurring since the previous visit will be checked and recorded in the eCRF, as well as the related concomitant medications. Any AE occurring during the study visit must also be monitored and recorded in the eCRF;
- Pregnancy test: urine samples will be collected from childbearing potential female subjects for pregnancy testing, according to [Section 7.3.5](#);
- Physical examination: a full physical examination will be performed and any new CS abnormality revealed since TP1 will be recorded as an AE;
- 12-lead ECG: a single ECG will be recorded to assess ECG parameters (HR, PR, QRS and QTcF), according to [Section 7.3.3](#). The assessment will be performed in pre-dose: within 1 h before T0; and in post-dose: 45 min, 1 h 45 min and 2 h 45 min after T1;
- Blood pressure: SBP and DBP will be measured after 5 min in supine position, as described in [Section 7.3.2](#). The assessment will be performed before or after the 12-lead ECG assessment, in pre-dose: within 1 h before T0; and in post-dose: 45 min, 1 h 45 min and 2 h 45 min after T1;
- Lung function: serial spirometries will be performed according to [Section 7.3.1](#). For each subject, the assessments will start at approximately the same time of the day as at TP1. Spirometry assessments will be collected in pre-dose: 45 min and 15 min before T0; and in post-dose: 5 min, 15 min, 30 min, 1 h, 1 h 30 min and 3 h after T1;
- Study treatment administration: single-dose (██████████) administration of the second propellant (based on each subject's randomisation arm, following a cross-over design), according to [Section 6.2.3](#). For each subject, treatment administration will start at approximately the same time of the day as at TP1;
- ██████████

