- The mean use (puffs) of rescue medication in the 3 h post-dose will be summarised for each treatment, using descriptive statistics.

The safety variables assessing the **secondary objective** of the study (i.e. general safety and tolerability of the two different propellants) will be analysed as follow:

- **Adverse events and adverse events of particular interest:**

All AEs starting on or after the time of first study treatment intake will be classified as treatment-emergent adverse events (TEAE). Any AEs started after the informed consent signature and before the time of first study treatment intake will be classified as pre-treatment AEs.

The number of subjects who experienced at least one TEAE, ADR, serious TEAE, serious ADR, TEAE leading to study discontinuation, and TEAE leading to death will

|  |                      |
|--|----------------------|
| Clinical Study Code No.: CLI-05993AB6-07 | Version No.: 2.0     |
| EUDRACT No.: 2022-000536-36              | Date: 30 August 2022 |

be summarised for each treatment. Summaries will be presented overall (number and percentage of subjects having at least one event, total number of events) and by system organ class (SOC) and preferred term (PT) (number and percentage of subjects having at least one occurrence of that event) using the MedDRA. Specific summary tables will be provided for the AEs of particular interest (bronchospasm, cough, dysphonia, hoarseness).

All AEs will be listed.

Pre-treatment AEs will be listed only.

- **ECG**

For ECG parameters: HR, QRS, PR, and QTcF, mean absolute values and change from baseline will be summarised for each treatment using descriptive statistics. For QTcF, the following categories will also be analysed for each study treatment, by means of descriptive statistics:

- For male subjects: QTcF interval >450 ms, >480 ms and >500 ms;
- For female subjects: QTcF interval >470 ms and >500 ms;
- For both, male and female subjects: Change from baseline >30 ms and >60 ms.

The analysis will be presented at each post-dose timepoint and at any post-dose timepoint.

All data will be listed.

- **Vital signs**

Vital signs (SBP and DBP) mean absolute values at each pre-dose and post-dose timepoint and change from baseline will be summarised for each study treatment, by means of descriptive statistics.

All vital signs will be listed.

|              |
|--------------|
| • [REDACTED] |
| [REDACTED]   |
| • [REDACTED] |

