2. SAFETY ANALYSES

2.1 ADVERSE EVENTS

2.1.1 *Available data*

Adverse events (AEs) are coded into system organ classes and preferred terms using the medical dictionary for regulatory activities (MedDRA). For each AE, start and stop date(time)s are collected as well as severity, a seriousness flag, treatment-relationship, action taken towards the study drug and outcome.

2.1.2 *Derivation rules*

Pre-treatment AEs are defined as AEs starting between date of informed consent with 00:00 added as time part and the date(time) of first study drug administration – 1 minute, extremes included.

Treatment-emergent adverse events (TEAE) are defined as AEs starting on or after first administration of any study drug.

Adverse drug reactions (ADRs) are defined as TEAEs related to study drug or with missing relationship.

AEs of particular interest will be selected based on the following algorithms:

- Bronchospasm: to select preferred terms or lowest level terms including the word “bronchospasm”
- Cough: to select preferred terms or lowest level terms including the words “cough” or “coughing”
- Dysphonia: to select preferred terms including the word “dysphonia” (excluding lowest level terms containing the word “hoarseness”)
- Hoarseness: to select lowest level terms containing the word “hoarseness”

Based on their start date(time), AEs will be allocated to the phase and period during which they started. Phases and periods are defined in section 5.2.1. In case the AE start date(time) is incomplete or missing and the AE could consequently be allocated to more than one phase or period, a worst-case allocation will be done as detailed below:

- Treatment phase vs. non-treatment phase: AE will be allocated to the treatment phase.
- Multiple treatment periods: AE will be allocated to all treatment periods, except periods for which the available parts of the AE start or stop date(time) provides evidence the AE did not occur during that period.

A fatal AE is defined as an AE with outcome ‘fatal’.

An AE for which the study drug was discontinued is defined as an AE with action taken ‘drug permanently withdrawn’.

	Statistical Analysis Plan	
CLI-05993AB6-07		Final 1.0 of 22DEC2022

AE onset and duration will be calculated as follows:

- AE onset day (vs. first administration) =
 - AE start date < date of first administration: AE start date – date of first administration
 - AE start date \geq date of first administration: AE start date – date of first administration + 1 day

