2.1.3 Presentation of results

Tables will present TEAEs only. Pre-treatment AEs will only be listed.

An overview table will show the number and percentage of subjects with at least one event and the number of events by treatment and overall for the following:

- TEAEs
- Serious TEAEs
- Non-serious TEAEs
- ADRs
- Serious ADRs
- Severe TEAEs
- TEAEs leading to study drug discontinuation
- TEAEs leading to death
- TEAEs of particular interest

Separate summary tables by MedDRA system organ class and preferred term will show the number and percentage of subjects with at least one event and the number of events by treatment and overall for the aforementioned categories. Each AE record in the clinical database is considered as a distinct adverse event and is counted as such. Blank system organ classes and preferred terms, if any, will be shown as ‘Not Available’ in the tables and listings.

	Statistical Analysis Plan	
CLI-05993AB6-07		Final 1.0 of 22DEC2022

All AEs, including pre-treatment events and all coding information will be listed. COVID-19 related AEs will be flagged. Separate listings will be prepared for the categories presented in the summary tables.

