5.2 PHASES, PERIODS AND TIME POINTS

5.2.1 *Phases and periods*

Adverse events, medications, and procedures will be allocated to phases and periods. All other analyses will not be allocated to phases and periods. Instead, the visit and time point labels indicated on the subject's case report form (CRF) will be used to allocate the assessments to the correct treatment. Early termination and follow-up visit assessment will be allocated to the last administered treatment.

Adverse events and medications:

Phase	Period	Start	End
Screening		Date of signing the informed consent form (ICF), with 00:00 added as time part	First administration date(time) in period 1 – 1 minute
Treatment	Period 1	First administration date(time) in period 1	First administration date(time) in period 2 – 1 minute
	Period 2	First administration date(time) in period 2	Date of last contact, with 23:59 added as time part

Per definition, and for each subject, the first phase starts on the date of the earliest available ICF signature, with 00:00 added as time part. The last available phase/period ends on the date of last contact, with 23:59 added as time part.

Procedures:

Phase	Period	Start	End
Screening		Date of signing the informed consent form (ICF)	First administration date in period 1 – 1 day
Treatment	Period 1	First administration date in period 1	First administration date in period 2 – 1 day
	Period 2	First administration date in period 2	Date of last contact

Per definition, and for each subject, the first phase starts on the date of the earliest available ICF signature. The last available phase/period ends on the date of last contact.

All tables and figures will present treatments/sequences rather than periods.

AEs, medications and procedures will be allocated to phases and periods as described in sections 2.1.2 and 4.5.2 respectively.

	Statistical Analysis Plan	
CLI-05993AB6-07		Final 1.0 of 22DEC2022

5.2.2 *Baseline and change from baseline*

The baseline value is a non-missing value before the first administration of any study drug.

The following table summarizes the baseline definition for each parameter:

Parameter	Baseline
Vital signs	Day 1 pre-dose (of each treatment period)
ECG parameters	Day 1 pre-dose (of each treatment period)
Lung function	Day 1 pre-dose (average of 45 min and 15 min pre-dose measurements of each treatment period)

Note: decisions on whether a different baseline should be used in the analysis will be fully documented in the DRR.

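### TEAE status and period are set by start time alone, and the plan does not say how a recorded AE that worsens after a dose is entered

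*Protocol*

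**What the plan says.** **Definition.** Protocol 12.3.6 splits AEs at the first dose by when they started. On one side: "All AEs starting on or after the time of first study treatment intake will be classified as treatment-emergent adverse events (TEAE". On the other: "Any AEs started after the informed consent signature and before the time of first study treatment intake will be classified as pre-treatment AEs". SAP 2.1.2 repeats the rule: "Treatment-emergent adverse events (TEAE) are defined as AEs starting on or after first administration of any study drug". None of the three sentences mentions worsening.

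**ADRs.** SAP 2.1.2 makes them a subset: "Adverse drug reactions (ADRs) are defined as TEAEs related to study drug or with missing relationship".

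**Period.** SAP 2.1.2 again goes by start: "Based on their start date(time), AEs will be allocated to the phase and period during which they started". In the phase table of SAP 5.2.1, period 1 closes at "First administration date(time) in period 2 – 1 minute", so the whole wash-out belongs to the first propellant.

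**Tables.** SAP 2.1.3 restricts them to TEAEs: "Pre-treatment AEs will only be listed".

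**Recording.** For the second dosing visit, protocol 7.1.4 says "the status of AEs ongoing at TP1 will be checked and updated in the eCRF when applicable". Section 7.1.3 has the matching instruction for AEs ongoing from screening. Both sections ask for a fresh entry only for a new AE or one occurring during the visit. Protocol 10.8 requires clinically significant (CS) changes at later visits to be reported as AEs. It does not say that a change in an AE already on the AE page gets a second record.

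**The concern.** The AEs of particular interest are bronchospasm, cough, dysphonia and hoarseness. In subjects with asthma, one of these can arise after consent, still be present at a dosing visit, and get worse after the inhalations. Such a worsening is relevant to the tolerability comparison between the propellants.

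Under a start-only rule, the fate of that event depends on a recording choice that the plan leaves open. If the site updates the existing record, the old start time decides the classification, whatever happened after the dose. Approximately 4 centres take part, and they could enter the same clinical course in different ways. The by-treatment AE tables would then partly reflect record-keeping.

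**Working it through.** The point concerns a rule, so there is no figure in the plan to reproduce. The check is to run each possible course of an AE through SAP 2.1.2, 2.1.3 and 5.2.1, once for each way of recording it.

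| Course of the AE | Existing record updated | New record opened at the worsening |
|---|---|---|
| Arises between consent and the TP1 dose, worsens after the TP1 dose | Pre-treatment; listing only | New record is a TEAE under the first propellant |
| Arises between consent and the TP1 dose, worsens after the TP2 dose | Pre-treatment; listing only | New record is a TEAE under the second propellant |
| Arises after the TP1 dose or in the wash-out, worsens after the TP2 dose | TEAE under the first propellant only; updated severity, seriousness or relatedness appears there | Existing record stays with the first propellant; new record counts under the second |
| Condition already present at consent, worsens after a dose | Does not apply: it is held as medical history or concomitant disease, so there is no AE record to update | If reported as an AE, it is a first record with a post-dose start, hence a TEAE under that propellant |

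The gap is confined to the first three rows, middle column.

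**What the first two rows lose.** A record classed as pre-treatment is outside every category tabulated in SAP 2.1.3: all TEAEs, serious, severe, ADR and particular interest. It is also outside the matching listings. Listing 16.2.7.10, for example, is limited to TEAEs. The event appears only in the pre-treatment listing (16.2.7.1).

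**What the third row loses.** The AE did begin after the first propellant, so its count there is right. What is missing is a count for the second propellant. In addition, a severity or relatedness that was raised after the second dose is shown under the first.

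**Which way of recording the plan implies.** Sections 7.1.3 and 7.1.4 point to updating. SAP 2.1.1 names severity once per AE and mentions no date on which severity changed. Section 10.8 points the other way for clinically significant changes. No passage settles it.

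**Exposure windows.**
- Consent to TP1: up to 7 days from pre-screening to screening, plus up to 21 days from screening to TP1, so 7 + 21 = 28 days as scheduled.
- TP1 dose to TP2 dose: 2 to 7 days.

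**Size of one event.**
- With all 24 randomised subjects dosed in a period: 1/24 = 4.2 percentage points; 2/24 = 8.3.
- With 20 subjects in the denominator: 1/20 = 5.0 percentage points.

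**Frequency.** An expected count would need two rates: the share of subjects who carry a recorded AE into a dosing visit, and the share of those whose AE then worsens. The documents give neither, so no expected number is offered.

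**The case against.** The strongest reply is that worsening can already reach the tables. Protocol 10.8 makes reporting of clinically significant changes mandatory, 7.1.3 and 7.1.4 require AEs occurring during the visit to be recorded, and SAP 2.1.3 counts every AE record as a distinct event. A worsening entered that way has a post-dose start and falls under the correct propellant. Rules on splitting records may also sit in eCRF instructions that are not part of these documents. This stands in part: the loss is conditional on how the site records the event. It does not close the gap, because 10.8 is silent on AEs already recorded and the visit sections say to update them.

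Several stronger readings are tempting, and the documents do not support them:

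- **That any asthma symptom present before dosing hides a later worsening.** Conditions pre-existing at consent are recorded as medical history or concomitant disease (protocol 7.1.2, SAP 4.4), so they hold no AE record with an early start.
- **That events are charged to the wrong propellant.** An AE that began after the TP1 dose belongs to that propellant. The fault is the missing second count and the misplaced update.
- **That worsening wheeze drops out of the particular-interest table because of this rule.** The SAP 2.1.2 term search does not select wheeze, whenever it starts.
- **That the trial's main question is affected.** Bronchoconstriction is judged by FEV1, the count of falls beyond 15%, PEF and rescue use. Lung function uses a baseline from each period, and none of these measures uses the TEAE definition.

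It is also fair to say that the affected group is narrowed by design. ACQ-5, recent exacerbation and lower respiratory infection are re-checked at randomisation, and a visit is postponed after an exacerbation that needs treatment. All AEs, including pre-treatment ones, are listed. SAE reporting to the sponsor runs from consent and does not depend on TEAE status.

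**Conclusion.** The point holds in a conditional form. Protocol and SAP agree with each other, and both lack a worsening clause. Together with the instruction to update ongoing AEs, this means that a post-dose worsening kept as one record is either absent from all AE tables (onset before the TP1 dose) or credited to the first propellant alone (onset between the two doses).

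The effect is limited to descriptive tables for the secondary safety objective. Each affected subject moves an incidence by about 4 to 5 percentage points, depending on whether 24 or 20 subjects are in the denominator. The conclusion assumes that the site does not open a new record and that no unseen eCRF instruction tells it to. It makes no claim about how often this will occur.

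**What to change.** 1. In protocol 12.3.6 and SAP 2.1.2, define a TEAE as an AE that starts, or worsens in severity or seriousness, on or after the first study treatment intake.
2. Tell sites, in protocol 7.1.3, 7.1.4 and 10.8 and in the eCRF completion guide, to enter a worsening after either dose as a new AE record with its own start date and time. Without that time the definition cannot be programmed, because the SAP describes no date of severity change.
3. In SAP 2.1.2, allocate the new record to the period in which the worsening began, and keep the existing record in its own period.

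The ADR, severe, serious and particular-interest tables then follow without redesign. The cost is a sentence or two in each document and a line in the completion guide. AE counts may rise slightly, since one clinical course can produce two records.

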### 12.3.8 Interim Analysis

No interim analyses are planned.

## 13. ETHICS COMMITTEE

The study proposal will be submitted to the EC in accordance with the UK requirements.

The EC shall give its opinion in writing, clearly identifying the study number, study title and ICF approved; before the clinical trial commences.

A copy of all communications with the EC will be provided to the Sponsor.

The Investigator should provide written reports to the EC, annually or more frequently if requested, on any changes significantly affecting the conduct of the trial and/or increasing risk to the subjects (according to the UK requirements).

|  |                      |
|--|----------------------|
| Clinical Study Code No.: CLI-05993AB6-07 | Version No.: 2.0     |
| EUDRACT No.: 2022-000536-36              | Date: 30 August 2022 |

## 14. REGULATORY REQUIREMENTS

The study will be notified to (or authorised by) the Health Authorities according to the legal requirements in the UK.

Selection of the subjects will not start before the approval of the EC has been obtained and the study has been notified to (or authorised by) the Health Authorities.

## 15. INFORMED CONSENT

The informed consent must be written in a language understandable to the subjects. It is the responsibility of the Investigator to obtain written consent from each subject prior to any study-related procedures taking place, by using the latest EC-approved version of the document.

Adequate time shall be given to the subject to enquire the Investigator about any clarification needed and to consider his/her decision to participate to the trial.

Consent must be documented by the subject's dated signature. The signature confirms that the consent is based on information that has been understood. Moreover, the Investigator must sign and date the informed consent form (ICF). A subject's inclusion in the study, as well as the processing of his/her data is based on subject's explicit consent, as pointed out within the informed consent.

In case of rescreening, the subject should sign a new informed consent and will be assigned with a new subject number. A link to prior subject number will be recorded in the eCRF.

Female subjects becoming pregnant during the study and partner of a subject participating to the study becoming pregnant will have to sign a specific informed consent form to provide permission to Chiesi to collect information about the pregnancy, its outcome and the birth and health of the newborn child.

Each subject's signed informed consent must be kept on file by the Investigator. One copy must be given to the subject.

## 16. SOURCE DOCUMENTS/DATA

### 16.1 Recording of Source Data

Data collection is the responsibility of the clinical trial staff at the site under the supervision of the site Investigator. The Investigator is responsible for ensuring the accuracy, completeness, legibility, and timeliness of the data reported. All source documents should be completed in a neat, legible manner to ensure accurate interpretation of the data.

Data recorded in the eCRF derived from source documents should be consistent with the data recorded on the source documents.

### 16.2 Direct Access to Source Document/Data

The Investigators or designated personnel must permit trial-related monitoring, audits, EC review or regulatory inspection, providing direct access to source data/documents.

## 17. STUDY MONITORING

Monitoring will be performed by █ who has been designated by Chiesi.

It is understood that the monitor(s) will contact and visit the Investigator/centre before the study, regularly throughout the study and after the study had been completed, and that they will

|  |                      |
|--|----------------------|
| Clinical Study Code No.: CLI-05993AB6-07 | Version No.: 2.0     |
| EUDRACT No.: 2022-000536-36              | Date: 30 August 2022 |

be permitted to inspect the various study records: eCRFs, Investigator study file and source data, provided that subject confidentiality is respected.

The purposes of these visits are:

- To assess the progress of the study;
- To review the compliance with the study protocol;
- To discuss any emergent problem;
- To check the eCRFs for accuracy and completeness;
- To validate the contents of the eCRFs against the source documents;
- To assess the status of drug storage, dispensing and retrieval.

Prior to each monitoring visit, the Investigator or staff will record all data generated since the last visit on the eCRF. The Investigator and/or study staff will be expected to be available for at least a portion of the monitoring visit to answer questions and to provide any missing information.

It is possible that the Investigational sites may be audited by Sponsor personnel or regulatory national and/or international regulatory agencies during and after the study has been completed.

